# **10.2 Secondary Efficacy Analyses**

The secondary efficacy endpoints are as follows:

- Peak-to-peak pressure gradient (ventricle to arterial or arterial to arterial) < 20 mmHg after stent placement, when applicable.
- Successful stent re-dilation (when indicated) at re-catheterization, defined as an increase in the intra stent angiographic luminal diameter of within 2mm of the adjacent native vessel diameter immediately after re-dilation.

# 11 Safety Analyses

#### **11.1 Primary Safety Analysis**

The primary safety endpoint will be assessed as the percentage of cases with freedom from procedure- or device-related SAEs resulting in an event listed below, with the performance goal defined as greater than 78% of cases:

- o Death
- o Cardiac arrest and/or emergency ECMO cannulation
- o Stroke
- o Limb loss
- Vessel dissection of target lesion
- Device thrombosis/occlusion
- Cardiac perforation requiring percutaneous or open surgical intervention
- Persistent cardiac arrhythmia requiring a pacemaker

The AT patient population will be used to test this hypothesis. The Clopper-Pearson method will be used to calculate the two-sided 95% confidence limits. If the lower limit of the resulting confidence interval exceeds 78%, then the null hypothesis will be rejected in favor of the alternative. The study hypothesis will be tested without imputation of missing data; however, additional sensitivity analyses will be performed to evaluate the effect of missing data on the study conclusions.

#### **11.2 Secondary Safety Analysis**

The secondary safety endpoints will be assessed:

- Free from stent embolization or migration through 6 months.
- Free from stent fracture that led to reintervention through 6 months
- Free from non-elective Minima Stent explant at 90-days post re-dilation
- Free from procedure- or device-related SAE during re-dilation that results in the following:
  - o Death
  - o Cardiac arrest and/or emergency ECMO cannulation
  - o Stroke
  - o Limb loss
  - Vessel dissection of target lesion
  - Device thrombosis/occlusion
  - Cardiac perforation requiring percutaneous or open surgical intervention
  - Persistent cardiac arrhythmia requiring a pacemaker

# **11.3 Adverse Events**

The summary statistics will be produced in accordance with section 9.

The following tables will be generated:

- All-Cause Mortality: A table of all anticipated and unanticipated deaths due to any cause, with number and frequency of such events in each arm/group of the clinical study.
- Serious Adverse Events: A table of all anticipated and unanticipated serious adverse events, grouped by organ system, with number and frequency of such events
- Other (Not Including Serious) Adverse Events: A table of anticipated and unanticipated events (not included in the serious adverse event table) grouped by organ system, with number and frequency of such events.

The number of events as well as the number of patients with each event will be summarized by time interval, The time intervals will be 0 to 30 days, 31-90 days and 91 to 180 days, 180 to 365 and annually through 5 years. The denominator will include all subjects in the AT population with follow-up data during the specific time interval.

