#### 6.3 Study Assessments

Activity	Screening	Procedure	Post-Procedure	1 Month (±7days)	3 Months (±7days)	6 Months ±14 days)	12 Months (±30days)	Annually Years 2-5 (±45days)
Informed consent & HIPAA authorization	Х							
Inclusion/exclusion criteria assessment	Х							
Demographics	Х							
Medical history	Х							
Physical exam & vital signs	Х		X	X	X	X	X	X
WBC, Hgb, Hct, platelets	$X^1$							
Serum creatinine	$X^1$							
INR (if taking Warfarin)	Х							
Chest X-ray	Х		X	X	X	X		
Transthoracic echocardiogram	Х		X	X	X	X	X	Х
Concomitant medications	Х	X	X	X	X	X	X	X
Minima stent implantation		X						
Pre-and Post-implantation angiography and hemodynamic assessments (within procedure)		X						
Adverse events / Device deficiencies 		X	X	X	X	X	X	X
Concomitant procedures 	Х		X	X	X	X		
CT angiography						X 		

To reduce unnecessary blood draws from patients, blood work may be performed after successful completion of all other screening activities / in the catheterization lab prior to device introduction into the bloodstream.

 All AEs collected for 12 months post-transplant; after 12 months, see Section 8.2 for select AE reporting.

 See Section 8.8 for reporting of select concomitant medications/procedures.

 Catheter-based angiography can be performed in place of CT if clinically appropriate.

The table below defines the analysis time windows that correspond to the targeted visit time frame.

Visit (target day)	Lower bound (days)	Upper bound (days)
Month 1 (30)	2	60
Month 3 (90)	61	135
Month 6 (180)	136	270
Month 12 (360)	271	374

Analysis Time Windows

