#### Efficacy:

This is a one proportion study powered at 80% and a one-sided 2.5% significance. The published literature supports a procedural effectiveness rate of 87%. As there are no approved devices in the space, a non-inferiority margin of 10% was selected and is supported by the Renata Physician advisors.

Based on published data (Stanfill) the incidence of angiographic success during implantation is 87%. Clinically, it is generally believed that a procedural success rate greater than 77% is clinically acceptable. Therefore, we are adopting a performance goal of 77% for procedural effectiveness.

Based on the clinically acceptable rate of 77%, the hypothesis would then be written as the following:

Null Hypothesis (H0): Incidence of clinical success  $\leq$ 77%. Alternative Hypothesis (HA): Incidence of clinical success >77%. One-Sided (H0: P  $\leq$  P0 vs. H1: P > P0)

Assuming a clinical success rate of 97% (Boe), 24 subjects will provide 80% power to meet the performance goal and reject the null hypothesis at a 2.5% one-sided significance level. The sample size calculation was based on the normal approximation to the binomial distribution.

Co-Primary Endpoint Power Calculation:

For the study to successfully pass, all both Safety & Efficacy Primary Endpoints must reject their null hypothesizes concurrently, using the appropriate one-sided significance level for each endpoint (2.5% and 2.5% respectively); therefore, power calculations were performed for each hypothesis statement, based on the normal approximation to the binomial distribution, and combined using the Inclusion-Exclusion Rule (shown below), assuming the two endpoints are independent, to determine the power of the study at each sample size.

$$\begin{split} P(A \cup B) &= P(A) + P(B) - P(AB) \\ & Where: \\ P(A) &= \beta_{Efficacy} \\ P(B) &= \beta_{Safety} \\ P(AB) &= \beta_{Efficacy} \ x \ \beta_{Safety} \\ P(A \cup B) &= \beta_{Efficacy} \ \& Safety \\ Study \ Power &= 1 - \beta_{Efficacy} \ \& Safety \\ \end{split}$$

Using the assumptions above, analysis shows a minimum of 36 subjects will provide 90% power to meet both the primary efficacy and safety performance goals. To account for approximately 15% attrition rate, a maximum of 42 United States subjects (42=36(100%+15%)) will be allowed to be implanted, prior to further authorization.

Sample	Safety	Efficacy	Total
Size	Power	Power	Power
20	0.49	0.66	0.32
21	0.53	0.70	0.37
22	0.57	0.75	0.42
23	0.60	0.78	0.47
24	0.64	0.82	0.52

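### The adverse-event intervals in SAP 11.3 overlap at day 180, run past the end of full AE collection, and use an undefined denominator

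*SAP*

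**What the plan says.** SAP 11.3 lists three tables (all-cause mortality, serious AEs, other AEs) and then adds that "The number of events as well as the number of patients with each event will be summarized by time interval". The cut points follow: "The time intervals will be 0 to 30 days, 31-90 days and 91 to 180 days, 180 to 365 and annually through 5 years". Its rule for denominators is "The denominator will include all subjects in the AT population with follow-up data during the specific time interval". Section 11.3 does not say what counts as follow-up data. I read the interval rule as applying to all three tables, since it follows directly after them.

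Two parts of SAP 6.3 bear on this:

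- **Collection.** Footnote 2 of the schedule reads: "All AEs collected for 12 months post-transplant; after 12 months, see Section 8.2 for select AE reporting". SAP 8.2 is Analysis Populations and lists no adverse events. The protocol text supplied is a synopsis without such a section, so the list may stand in a part not seen here.
- **Visit timing.** Target days are 30, 90, 180 and 360. The allowed visit windows are 7 days either side at months 1 and 3 ("3 Months (±7days" for the latter), 14 days at month 6 ("6 Months ±14 days") and 30 days at month 12.

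**The concern.** There are three separate problems.

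1. **Overlap.** An event on day 180 satisfies two interval definitions. That day is the 6-month target, the visit at which CT or catheter angiography is scheduled, so imaging findings may be dated to it.
2. **Narrower collection.** After 12 months only select AEs are gathered, but the interval summary continues to year 5 without that limit. A drop after year 1 could come from collection alone and be read as long-term safety.
3. **Denominator.** The first three cuts (30, 90, 180) are also visit target days, and compliant visits may fall on either side of them. A child seen on days 28 and 93 has no visit in days 31-90, although the day-93 visit covers that whole period. If follow-up data means data dated in the interval, that child leaves the denominator when event-free, but stays in with an event, because the event is itself data.

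These tables are the SAP's main description of when harm occurs. The protocol synopsis allows Kaplan-Meier graphs as appropriate, but SAP section 11 plans none.

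**Working it through.** The plan gives no interval rate or count, so there is no figure on this point to reproduce. The illustrations use the SAP's maximum of 42: "To account for approximately 15% attrition rate, a maximum of 42 United States subjects" (36 x 1.15 = 41.4, rounded up).

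**Overlap.** One shared day is 1/90 = 1.1% of days 91-180 and 1/186 = 0.5% of days 180-365. This is the effect if events are spread evenly over days; clustering at the 6-month visit would raise it. The SAP's analysis windows in 6.3 meet without overlap (60/61, 135/136, 270/271), which suggests that the shared day is a drafting slip.

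**Collection.** Setting footnote 2 beside 11.3: full collection covers one of the five follow-up years, and the interval summary covers all five. Four of the five years are therefore reported under the narrower rule without a label.

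**Denominator read as a scheduled visit in the interval.** The allowed visit days are 23-37 (15 days), 83-97 (15 days), 166-194 (29 days) and, with target day 360, 330-390 (61 days). Assume that each visit day is uniform in its window and independent of the others. Then

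P(no visit in interval) = P(previous visit falls before it) x P(next visit falls after it).

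| Interval (days) | Calculation | Share of compliant children with no visit |
|---|---|---|
| 31-90 | 8/15 x 7/15 = 56/225 | 24.9% |
| 91-180 | 8/15 x 14/29 = 112/435 | 25.7% |
| 180-365, month 12 target day 360 | 14/29 x 25/61 = 350/1769 | 19.8% |
| 180-365, month 12 target day 365 | 14/29 x 30/61 = 420/1769 | 23.7% |

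*Upward example.* Take 42 fully followed children, 3 with an event in days 31-90. The true share is 3/42 = 7.1%. The 39 event-free children shrink to 39 x (1 - 56/225) = 29.3, the denominator becomes 32.3, and the table shows 3/32.3 = 9.3%.

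**Partly observed children counted in full.** The month 1 visit falls on days 31-37 with probability 7/15 = 46.7%. A child lost straight after such a visit enters the 31-90 denominator with at most 7 of 60 days observed.

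*Downward example.* Suppose 6 of 42 (14%, about the planned attrition) are lost just after the month 1 visit. Then 6 x 7/15 = 2.8 of them are counted on average, and the denominator is 36 + 2.8 = 38.8. With 3 affected children the table shows 3/38.8 = 7.7%, against 3/36 = 8.3% among those followed throughout.

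The same happens later. At the primary analysis, a late-enrolled child whose 6-month visit falls on days 180-194 (15 of the 29 allowed days) enters the 180-365 column with at most 15 of 186 days observed.

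**The case against.** A reader might infer that the rates in this table are wrong, and in particular that early rates are overstated. The documents do not support that.

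- **The 20-26% loss depends on one reading.** It arises only if follow-up data means a scheduled visit dated in the interval. The phrase can equally mean time under observation; the child seen on day 93 then stays in and the loss is zero. Against this, SAP 9 bases percentages on non-missing observations and SAP 6.3 reduces the sample size for missed collection, so a programmer could reasonably take the narrower reading. The ambiguity stands; the error is not shown.
- **Direction is not fixed.** Partly observed children pull the rate the other way.
- **Days 0-30 are essentially unaffected**, because AEs are also collected at the procedure and post-procedure.
- **Cutting at target days is not an error in itself.** AEs are ordinarily placed by onset date, and the cuts matter only with a visit-based denominator. Day 365 is not the SAP's month 12 target, which is 360.
- **The SAP does not state a double count on day 180.** Its labels permit one.
- **The later SAE columns may be complete** if the select list includes all SAEs. Columns for mortality and for the select AEs can be valid to year 5.
- **No decision rests on the table.** Primary safety in SAP 11.1 is a separate AT proportion with a Clopper-Pearson interval.

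All of this limits the point. It does not remove the overlap, the unlabelled change in collection or the undefined denominator.

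**Conclusion.** The point holds as a low-severity reporting defect with three parts.

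- The shared day 180 and the mismatch between five-year columns and 12-month full collection follow from the text alone. The mismatch affects other AEs, and SAEs unless all of them are on the select list.
- The denominator is undefined. Its effect ranges from no loss (time under observation) to about 20-26% of compliant event-free children per interval between days 31 and 365 (visit dated in the interval, with uniform and independent visit days).
- Partial exposure counted in full remains under both readings and can offset or reverse the first effect, so no direction of bias can be claimed.

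The primary safety test, alpha and power do not change.

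**What to change.** In SAP 11.3:

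1. Change the fourth interval to 181-365 and start the annual intervals on day 366.
2. Limit the other-AE interval table to 12 months, and the all-SAE interval table as well unless the select list contains all SAEs. Report years 2-5 in a separate table labelled as select AEs, with year 1 restricted to the same AEs for comparison. Correct the footnote's reference to Section 8.2 so that it names the document and place where the list stands.
3. Define the denominator as AT subjects still under observation at the start of the interval, and add event rates per person-time. Both are needed: a child last seen on day 92 still counts in full for days 91-180 under this denominator, and only person-time reflects the partial exposure.

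The cost is SAP wording, minor table programming and one extra table. No new data are needed.

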# **11.4 Clinical Laboratory Evaluations**

The summary statistics will be produced in accordance with section 9 and reported with the baseline characteristics.

#### **11.5 Prior and Concurrent Medications**

The summary statistics will be produced in accordance with section 9.

# 12 Subgroup Analyses

In or evaluate the consistency of the treatment results, the primary endpoints will calculated for each of the subgroups listed below. The fisher's exact test will be used to evaluate the statistical significance of any differences across subgroup levels for both primary endpoints.

Demographic/Baseline Characteristics

- Sex
- Age (<6mo; 6mo-24mo; >24mo)
- Race (Caucasian vs. Non-Caucasian)

Procedural:

• Implant location (Pulmonary vs. Aortic)

# **12.1 Geographic Region**

Should patients be enrolled outside the US, the primary endpoints will be compared across geographical region (e.g. US vs. Japan vs. Europe).

### **12.2 Investigational Sites**

Renata Medical will select investigators based on training and experience. Renata may select up to 8 US investigational sites, with the possibility of additional Japanese and/or European Union sites pending the appropriate regulatory approvals. These sites will enroll a maximum of 42 subjects with a minimum of 50% of the patients implanted being treated within the United States.

Results for the primary endpoints will be presented stratified by investigational site and rates will be compared using the fisher's exact test.

#### 13 Missing Data Considerations

The hypothesis tests for the primary endpoints will be performed without imputation of missing data. The incidence of missing data is expected to be low and all efforts will be made to collect all required data points in the study. Should there be missing data for either primary endpoint, then sensitivity analyses will be performed to evaluate the potential effect of the missing data on the study conclusions. If the study conclusions are upheld using a worst-case scenario imputation approach, then no further missing data analyses will be required. The worst-case scenario approach would treat all missing data points as failures for the endpoint.

If the results are not upheld with the worst-case scenario approach, then two further analyses will be performed.

- 1) A tipping point analysis: missing data are imputed over the range of possible scenarios, from imputing all as successes to all as failures, in order to determine at what point the hypothesis is no longer met.
- 2) Multiple Imputation: A multiple imputation analysis will be performed using a logistic regression model. Variables in the model will include:
  - a. Lesion Location (Aortic, Pulmonary)
  - b. Age
  - c. Weight

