#### **Inclusion Criteria for Re-dilation**

Candidates must meet one or more of the following inclusion criteria:

Development of an increase in the pressure gradient across the stent and/or stent lumen diameter less than the nominal adjacent vessel diameter, as defined as:

- 1. Peak Doppler echo gradient  $\geq$  30 mmHg and/or a mean Doppler gradient  $\geq$ 20 mmHg across the stented vessel
- 2. Stented lumen diameter is  $\leq$  75% of adjacent native vessel

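### The multiple-imputation model in SAP 13 names only baseline variables and leaves out the scheduled follow-up echo, so it adds little if missing 6-month imaging is related to re-narrowing

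*SAP*

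**What the plan says.** SAP 13 handles missing primary outcomes in steps.

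- Primary test: "The hypothesis tests for the primary endpoints will be performed without imputation of missing data".
- First sensitivity analysis: "The worst-case scenario approach would treat all missing data points as failures for the endpoint".
- If that overturns the conclusion: "If the results are not upheld with the worst-case scenario approach, then two further analyses will be performed". One is a tipping point in which "missing data are imputed over the range of possible scenarios, from imputing all as successes to all as failures". The other is item 2: "A multiple imputation analysis will be performed using a logistic regression model. Variables in the model will include" lesion location, age and weight. No measurement made after the implant is named.

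Three other places bear on this.

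- The SAP 6.3 schedule has a row "Transthoracic echocardiogram", marked post-procedure and at 1, 3 and 6 months, among other visits.
- SAP 6.2 (Inclusion Criteria for Re-dilation) opens with "Development of an increase in the pressure gradient across the stent and/or stent lumen diameter less than the nominal adjacent vessel diameter" and sets Doppler limits of 30 mmHg peak and 20 mmHg mean across the stented vessel.
- SAP 7 inflates the sample size: "To account for approximately 15% attrition rate", from 36 to 42.

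The efficacy component most exposed to missing data is the third one in SAP 10.1, the 6-month vessel diameter from CT angiography or angiography.

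**The concern.** Location, age and weight at baseline do not say how the stent is doing in a particular child. A child with a high gradient at 3 months and no 6-month image gets the same imputed chance of success as a child of the same location, age and weight with a normal echo. If the reason for the missing image is connected with re-narrowing, and the listed variables do not pick this up, the imputation inherits the bias of the complete-case analysis that it is meant to check.

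This matters because the tipping point shows how many imputed failures would reverse the result but not how many are plausible. Multiple imputation is the one step in SAP 13 that could bring each child's own data to that question.

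**Working it through.** **1. The plan's own figures.** Power = Φ((|p1 − p0| − 1.96·√(p0·q0/n)) / √(p1·q1/n)). With n = 36, efficacy (0.77 against 0.97) gives 0.986 and safety (0.22 against 0.04) gives 0.914. The product is 0.902, which matches the SAP 7 table (0.99, 0.91, 0.90). Attrition: 36 × 1.15 = 41.4, rounded up to 42, so 42 − 36 = 6 are expected to be missing.

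**2. Would the imputation be reached?** The SAP 10.1 rule is a Clopper-Pearson two-sided 95% lower limit above 77%.

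| Successes/n | Lower limit | Passes |
|---|---|---|
| 38/42 | 77.4% | yes |
| 37/42 | 74.4% | no |
| 36/42 | 71.5% | no |
| 33/36 | 77.5% | yes |
| 32/36 | 73.9% | no |

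Of 42 subjects, at most 4 may be missing or failed for the worst case to be upheld. With 6 missing and no observed failure it is 36/42 and fails. The complete-case test still passes with up to 3 failures in 36. At the planned attrition, every positive efficacy result therefore goes on to the tipping point and the imputation.

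**3. Expected bias if missingness follows the echo.** The documents give none of these inputs, so they are assumptions. A raised gradient flags 80% of failures and 10% of successes. The image is missing in 40% of flagged and 8% of other children. Location, age and weight are unrelated to outcome.

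- Missing among failures: 0.80 × 0.40 + 0.20 × 0.08 = 0.336.
- Missing among successes: 0.10 × 0.40 + 0.90 × 0.08 = 0.112.
- True success 77%: the complete-case rate is 0.77 × 0.888 / (0.77 × 0.888 + 0.23 × 0.664) = 0.684/0.836 = 81.7%. Expected missing: 42 × (0.77 × 0.112 + 0.23 × 0.336) = 6.9.
- True success 97%: 0.97 × 0.888 / (0.97 × 0.888 + 0.03 × 0.664) = 0.861/0.881 = 97.7%.
- Weaker marker (60%/15%) and weaker missingness (30%/10%), true success 77%: missing in 0.22 of failures and 0.13 of successes, so 0.77 × 0.87 / (0.77 × 0.87 + 0.23 × 0.78) = 78.9%.

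The complete-case bias is thus 4.7, 0.7 and 1.9 points respectively.

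**4. What the two imputation models do with it.** In simulations of 42 subjects on the 80%/10% and 40%/8% assumptions at true success 77%, the listed model gave about 81–82%, close to the complete-case value. A model containing the echo flag gave about 77–78%. In a simulation with the missingness reversed, so that children with raised gradients are imaged more often, the listed model gave 75.7% and the echo-informed model 77.0%. When missingness was unrelated to echo, the two agreed (76.7% and 76.8%).

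**5. A second simulation with a continuous gradient.** True success was about 90%, with about 14% missing, a Firth-penalised model, and the gradient added to the three listed variables. Assumed effects were log-odds of 1.5 per SD on outcome and 1.0 per SD on missingness. With no predictors and random missingness, small-sample shrinkage alone lowers the listed model by 0.9010 − 0.8902 = 1.1 points and the larger model by 0.9010 − 0.8878 = 1.3 points.

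| Driver of outcome and missingness | Full data | Complete case | Listed model | Listed plus gradient |
|---|---|---|---|---|
| Gradient | 90.0% | 91.6% | 90.5% | 89.0% |
| Age (1.0 per SD on each) | 90.1% | 91.5% | 89.3% | 89.1% |

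Adding the shrinkage back, in the gradient row the listed model stands at 91.6%, on the complete-case value, and the larger model at 90.3%, near the truth. In the age row the listed model stands at 90.4%, so it removes most of the bias.

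**The case against.** A reader might infer that the imputation simply repeats the complete-case result and cannot test it. The documents do not support that. Repetition requires location, age and weight to be uninformative. SAP 7 itself quotes different SAE rates by age (10% and 14%), SAP 12 pre-specifies age and implant location as subgroups, and the age row above shows the listed model correcting bias when age drives both outcome and missingness. Nor is the listed model the only check. The tipping point covers every possible set of missing outcomes: with 0, 1, 2 or 3 failures in 36, the result survives 4, 3, 2 or 1 failures among the 6 missing. The SAP's wording also does not strictly exclude further variables, but one chosen after the data are seen would not be pre-specified.

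A reader might also infer an inflated trial error rate. At true success 77%, imputation as listed meets the goal in 7–8% of simulated trials, with echo in about 3.5%, and with full data in 2.2%. The decision rests on the complete-case test, so these are not error rates of the trial. They also apply the exact limit at the mean imputed count. Allowing for between-imputation variance, a simplified run fell from 8.8% to 5.6%, about the complete-case rate of 5.8%.

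These objections also stand:

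- The direction of missingness is unknown. A raised gradient can lead to recatheterization, and catheter angiography may replace the 6-month CT, so such children may be imaged more often. The echo-informed model corrects that direction too.
- The marker accuracy is assumed. The gradient limits sit beside a comparison with the adjacent vessel, whereas the endpoint compares with post-implant diameter, so growth could raise a gradient without an endpoint failure.
- At high success rates the echo model may be slightly conservative. At true success 95%, among trials where the primary test passes and the worst case fails, it agrees with the primary result in 91%, against 97% on full data and 100% as listed.
- With about one failure expected in 36 at 97% success, an added strong predictor invites separation.

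**Conclusion.** The point holds as a gap in a sensitivity analysis. The listed imputation model ignores the post-implant information most relevant to the missing diameter, and at the planned attrition the step would be reached. Under the stronger assumptions at true success 77%, the estimate is about 4 points too high as listed and within about 1 point of the truth with echo. Under the weaker assumptions the complete-case bias left to correct is 1.9 points. At the planned 97% it is 0.7 points and changes little. If missingness is unrelated to echo, there is no difference in the estimate.

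The size rests on assumed marker accuracy and missingness, and on the listed variables not capturing the link. That a gradient across the stent is recorded at each echo is inferred from the visit schedule and the re-dilation criteria. The primary test and the tipping point are untouched. The change is worth making because it is cheap and improves the analysis in the situation a sensitivity analysis exists for: a mediocre success rate with informative missingness.

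**What to change.** Amend SAP 13 item 2 for the efficacy endpoint, before the data are analysed:

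1. Add to location, age and weight the last available Doppler gradient across the stent up to the 6-month visit, or a yes/no for the SAP 6.2 echo criterion, taken before any re-dilation. Keep age: nothing in the documents shows that weight can stand in for it.
2. Fit the model with a penalised or weak-prior logistic regression, because few failures are expected.
3. Count a child with an observed failure on either of the first two components as a failure, and impute only the missing diameter component.

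No new visits or tests are needed. The cost is SAP wording and slightly more programming. The imputed result may be less favourable, and some children will have only an early echo to contribute. The sponsor must confirm that the gradient is recorded at each echo.
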